13.5.1 Historical Control

Patients in this population defined by the eligibility criteria receive standard-of-care which consist of blood product support as needed and growth factor support with each cycle. Based on provided historical information, the overall response rate in this patient population receiving standard-of-care is 50%. It is anticipated that treatment with carfilzomib added to standard R-ICE will increase the overall response rate beyond the clinically significant rate of 70%.

13.5.2 Phase Ib Decision Rules

Let π represent the proportion of the evaluable population of interest who experience an overall response within 3 weeks after completion of therapy (i.e., 3 cycles) at the carfilzomib MTD. If the response rate of less than 50% is considered unacceptable. A response rate of more than 70% is considered promising and evidence of such will deem the treatment worthy of further study. The null and alternative hypotheses corresponding to the design are

$$H_0 : \pi \leq 50\%,$$
$$H_a : \pi > 50\%.$$

A total of up to 30 evaluable patients will be accrued in the Phase I and Phase Ib portions of the study. The evaluable population is defined as patients who meet eligibility requirements and complete at least 1 cycle of therapy. Unevaluable patients will be replaced.

With this re-design, the probability is 4.8% of falsely concluding that the proportion of those who experience an overall response exceeds 50% and 80.1% is the probability of correctly concluding efficacy when the overall response rate is 70%.

In the event that the actual first stage sample size is not as planned, the adjustment of the first-stage stopping rule will be based on the approximate minimax rule proposed in Green and Dahlberg (1992): Stop the trial if the number of responses is α or less, where α is the largest value for which power properties would be maintained given the attained first-stage sample size, assuming the planned final sample size is achieved and one applies the planned final boundary. If the planned second stage sample size is not attained, the bound will be adjusted so to preserve Type I error.

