Statistical Analysis	
 Phase I: The actual sample size for the Phase I population depends on the unknown dose-toxicity profile of the treatment and the maximum sample size is 21 patients. Phase Ib (Dose expansion cohort): The sample size calculation for the Phase Ib was based on testing the hypotheses concerning the proportion of the population who experience an objective response (i.e., CR or PR) described above. This design requires a total of up to 30 patients (it will include the patients treated in the Phase I phase and 9 patients enrolled in the dose expansion cohort). This will achieve approximately 80.1% power to detect differences of 20 percentage points (50% versus 70%). 
The primary objective of the Phase I part of this study is to determine the MTD

of the proposed regimen defined as the dose of carfilzomib added to standard R-ICE chemotherapy. The basic design of the Phase I trial will utilize a standard 3+3 dose-finding scheme which is a special case of the A + B design described by Lin and Shih (2001). Rationale behind the design is nested in the assumption that both the probabilities of toxicity and efficacious response are continuous monotonic non-decreasing functions of the dose.

The objective of the Phase Ib component is examination of the efficacy and toxicity of the addition of carfilzomib to R-ICE at the MTD dose.

The primary objective of the Phase Ib component is to assess the efficacy of the study treatment arm as compared to historical control. The primary efficacy endpoint will be best overall response rate (PR+CR) within following 3 cycles of C-R-ICE therapy (as demonstrated by whole body PET-CT and dedicated CT scans following Cycle 3 of therapy).

PK/PD Analysis: A pharmacologically-driven PK/PD model will be developed to elucidate the temporal relationship between carfilzomib concentrations and the time course of proteasome inhibition, along with temporal relationships with thrombocytopenia and neutropenia. This model will allow assessment of the dose and schedule at which carfilzomib facilitates maximal proteasome inhibition and thus lead to an increase response rate, while modulating the degree of severe toxicities. In addition, the effect of concomitant administration of rituximab, ifosfamide, carboplatin, and etoposide will be incorporated into the model to assess their potential effects on efficacy and/or toxicity.

INVESTIGATOR STUDY ELIGIBILITY VERIFICATION FORM

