13.1.2 Phase Ib

The sample size calculation for the Phase Ib population is based on testing the hypotheses concerning the proportion of the population who experience an objective response (i.e., CR or PR) described above. This design requires a total of up to 30 patients in order to achieve approximately 80.1% power to detect differences of 20 percentage points (50% versus 70%).

Based on the excellent response observed in the patients treated in the Phase I portion (ORR 90%) and budget changes, the sample size for the Phase Ib portion was reduced. The phase Ib portion will include 9 additional patients. The efficacy analysis will include evaluable patients in the Phase I and Phase Ib portions combined (sample size up to 45). The sample size calculation for the efficacy analyses is based on testing the hypotheses concerning the proportion of the population who experience an objective response (i.e., CR or PR) described above. This design requires a total of up to 30 patients in order to achieve approximately 80.1% power to detect differences of 20 percentage points (50% versus 70%).

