13.3 Descriptive Analyses

Measured outcome variables will be summarized overall and by relevant demographic and baseline variables. Descriptive statistics such as frequencies and relative frequencies will be computed for all categorical variables. Numeric variables will be summarized using simple descriptive statistics such as the mean, standard deviation and range. A variety of graphical techniques will also be used to display data, ex. histograms, boxplots, scatterplots, etc.

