13.4 Phase I

The primary objective of the Phase I part of this study is to determine the MTD of the proposed regimen defined as the dose of carfilzomib added to standard R-ICE chemotherapy which, if exceeded, would put the patient at an undesirable risk of medically unacceptable, DLTs experienced during treatment with C-R-ICE within the treated patient population. The definition of a DLT is in **Section 7.4.1**.

The basic design of the Phase I trial will utilize a standard 3+3 dose-finding scheme which is a special case of the A + B design described by Lin and Shih (2001). Rationale behind the design is nested in the assumption that both the probabilities of toxicity and efficacious response are continuous monotonic non-decreasing functions of the dose.

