13.5 Phase Ib (expansion cohort)

The objective of the Phase Ib component is examination of the efficacy and toxicity of the addition of carfilzomib to R-ICE at the MTD dose.

The primary objective of the Phase Ib component is to assess the efficacy of the study treatment arm as compared to historical control. The primary efficacy endpoint will be best overall response rate (PR+CR) within following 3 cycles of C-R-ICE therapy (as demonstrated by whole body PET-CT and dedicated CT scans following Cycle 3 of therapy).

The efficacy analysis will include patients treated in the Phase I and Phase Ib part of the study. This change in the protocol was decided based on the excellent ORR observed in the first 15 patients treated in the Phase part of the study and changes in the protocol budget.

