13.5.3 Secondary Analyses

Both efficacy and toxicity rates will be estimated using simple relative frequencies. The corresponding 95% confidence intervals for the estimated probabilities will be computed using the method proposed in Clopper and Pearson (1934). The relationship between binary outcomes and collected demographic and baseline variables will be statistically assessed using logistic regression in an exploratory fashion. Maximum likelihood estimation will be utilized in the model fitting procedures as implemented by SAS PROC LOGISTIC. Wald tests of the model effects will be performed to assess statistical significance; see SAS documentation for details. See Hosmer and Lemeshow (2000) for a discussion of such techniques. Alternative parametric models will be considered if model fit is found to be inadequate.

The estimated distributions of overall and progression free survival will be obtained using the Kaplan-Meier method. Estimates of quantities such as median survival will be obtained. Corresponding confidence intervals using the methodology of Brookmeyer and Crowley (1982) will be computed. It is assumed a priori that any drop out times will be non-informative in terms of the censoring mechanism. Groups defined by levels of categorical or dichotomized numeric demographic/baseline variables will be compared in regards to time-to-event distributions using the log-rank test. Cox proportional hazards model regression will be utilized for multivariate analyses.

All tests will be two-sided and tested at a 0.05 nominal significance level. Standard diagnostic plots will be used to assess model fit and transformations of variables may be considered in order to meet statistical assumptions.

The analysis will be performed using the SAS® statistical software system.

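### The hypotheses concern the response rate at the MTD, but the test pools all Phase I and Phase Ib dose levels, and no response rate at Dose Level 6 or by dose level is required

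*Combined protocol and SAP*

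**What the plan says.** Section 13.5.2 defines π, on which H0 (π ≤ 50%) and Ha (π > 50%) are stated, as the proportion with "overall response within 3 weeks after completion of therapy (i.e., 3 cycles) at the carfilzomib MTD". Section 13.5, like the synopsis, gives the Phase Ib objective as "examination of the efficacy and toxicity of the addition of carfilzomib to R-ICE at the MTD dose". Section 4.1 places Phase Ib at Dose Level 6.

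The analysis set is wider. Section 13.5: "The efficacy analysis will include patients treated in the Phase I and Phase Ib part of the study". Section 13.1.2: "The efficacy analysis will include evaluable patients in the Phase I and Phase Ib portions combined". The synopsis says of the 30-patient design that "it will include the patients treated in the Phase I phase and 9 patients enrolled in the dose expansion cohort". The evaluable population in 13.5.2 requires eligibility and one completed cycle, with no condition on dose.

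On reporting, Section 13.3 says "Measured outcome variables will be summarized overall and by relevant demographic and baseline variables", and Section 13.5.3 says "Both efficacy and toxicity rates will be estimated using simple relative frequencies", with Clopper-Pearson intervals and exploratory regressions on demographic and baseline variables. Neither section names dose level. Section 13.4 rests the Phase I design on the assumption that "both the probabilities of toxicity and efficacious response are continuous monotonic non-decreasing functions of the dose".

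**The concern.** Phase I is a 3+3 escalation, so the pooled set can contain patients treated below the dose carried into Phase Ib. The test then concerns a rate averaged over dose levels, weighted by cohort size, while the hypotheses name the rate at one dose. Section 13 says the analyses focus on estimating parameters for planning larger comparative trials. A trial planned at the Phase Ib dose needs the response rate at that dose, and the plan as written need never report it. A reader of the pooled result could not tell whether it understates or overstates the Level 6 rate.

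**Working it through.** **The plan's own figure.** Section 13.5.2 gives 4.8% type I error and 80.1% power at 50% versus 70%, with up to 30 patients, but no success boundary. With S ~ Bin(30, π), the smallest exact boundary with one-sided error of at most 5% is S ≥ 20: error 4.94% at 50%, power 73.0% at 70%. The stated pair is not reproduced at 30. That is a separate matter; 20/30 is used here only as an inferred working boundary.

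**How many patients are below Level 6.** Sections 4.2 and 13 allow at most 21 Phase I and 9 Phase Ib patients. Table 2 requires at least 6 patients at the recommended dose. So at most 21 − 6 = 15 of 30 lie below Level 6, which also fits five lower levels of 3 patients (5 × 3 + 6 = 21). Actual cohort sizes are not given and the schema figure is not visible. I therefore use 6 to 15, holding the total at 30; the 6 is an assumed low end. I also assume that no one was treated above Level 6.

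**Formulas.** With m patients below Level 6 responding at rate pL, and 30 − m at Level 6 responding at p6:

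- expected pooled rate = [m·pL + (30 − m)·p6] / 30
- success = P(Bin(m, pL) + Bin(30 − m, p6) ≥ 20)

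For example, with m = 15, p6 = 0.7 and pL = 0.6: (15 × 0.6 + 15 × 0.7)/30 = 0.65. With m = 6: (6 × 0.6 + 24 × 0.7)/30 = 0.68.

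| Level 6 rate | Lower-dose rate | Expected pooled rate, m = 6 / m = 15 | Success, m = 6 / m = 15 |
|---|---|---|---|
| 70% | 70% | 70% / 70% | 73% / 73% |
| 70% | 60% | 68% / 65% | 65% / 51% |
| 70% | 50% | 66% / 60% | 55% / 29% |
| 70% | 90% | 74% / 80% | 87% / 98% |
| 50% | 50% | 50% / 50% | 4.9% / 4.9% |
| 50% | 60% | 52% / 55% | 8% / 13% |
| 50% | 70% | 54% / 60% | 11% / 29% |

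Rows 4, 6 and 7 contradict the Section 13.4 assumption.

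**Type I error under Section 13.4.** If response does not decrease with dose and the Level 6 rate is at most 50%, every lower level is also at most 50%. Success is then at most P(Bin(30, 0.5) ≥ 20) = 4.94%.

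**Sensitivity to the boundary** (m = 15, p6 = 0.7). For pL = 0.7, 0.6 and 0.5, success is 84.1%, 65.6% and 42.9% at 19/30, and 58.9%, 35.7% and 17.1% at 21/30. Over boundaries 19 to 21 the loss is 19 to 23 points for pL = 0.6 and 41 to 44 points for pL = 0.5, so it depends little on the boundary.

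**The case against.** Pooling is disclosed in the synopsis and in Sections 13.1.2 and 13.5, and it is defensible: 15 patients cannot carry the test (12/15 gives 1.8% error and 29.7% power). Section 3.2 states the response objective without naming the MTD, which fits the pooled set. All of this stands. It means the documents are mixed and need reconciling; it does not supply the missing Level 6 rate.

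The only response data in the plan are favourable. Section 13.1.2 reports a 90% response rate in Phase I, dose levels not stated, and Section 13.5 ties the change to the first 15 patients. On the inferred layout those 15 could all have been below Level 6. Lower-dose rates of 50% or 60% then look unlikely, and a reader should not infer that the trial faces a 22- or 44-point loss of power. That size also needs the maximum 15/15 split. With 90% at every level, success at 20/30 is practically certain.

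A reader might also infer that pooling inflates type I error for the MTD claim. Under the plan's stated assumption it does not. Nothing in the documents says that response falls with dose.

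The PK/PD work in Section 14.2 relates proteasome inhibition to efficacy. Its Phase I sampling is no defect, since planned dose varies only there. But it is a modelling exercise and does not require an observed response rate by dose.

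**Conclusion.** The point holds as a mismatch between the named parameter and the analysed set, together with a missing report. Under Section 13.4 the pooled rate can only understate the MTD rate: with Level 6 at 70%, by 2 to 5 points if lower doses respond at 60%, or by 4 to 10 points if at 50%. If the assumption fails, the pooled rate can overstate: by 4 to 10 points with lower doses at 90%. With a true Level 6 rate of 50% and lower doses at 60% or 70%, success is 8% to 13% or 11% to 29%, against 4.9%. The reported 90% makes the overstating direction worth showing, but is not evidence for it.

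These are scenarios, not forecasts. They rest on an inferred boundary, an inferred split and assumed rates. The mismatch and the missing Level 6 rate rest on the text alone. The documents do not support the stronger reading that the pooled test is invalid.

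**What to change.** 1. In Section 13.5.2, define π as the response rate across all carfilzomib dose levels treated in Phase I and Phase Ib. State that extending the conclusion to the MTD relies on the Section 13.4 assumption, and that this definition follows a pooling decision made after Phase I responses were seen.
2. In Section 13.5 and the synopsis, reconcile the MTD objective: efficacy at the MTD is addressed by the Level 6 estimate, and the historical-control test by the pooled set.
3. In Section 13.5.3, add the response rate at Dose Level 6 (Phase I Level 6 plus Phase Ib patients) with a 95% Clopper-Pearson interval, and a descriptive table by dose level giving n, responders, rate and interval. Classify patients by the level assigned at the start of Cycle 1, because Section 7.4.1 lets a patient with a DLT continue at a reduced level. Report both beside the pooled test in any efficacy statement about the MTD.

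The cost is a protocol amendment with IRB approval (Section 17.1), a few sentences and one table; no extra patients, visits or data. The Level 6 estimate will be imprecise (for example 11/15: 45% to 92%) and is for estimation, not a second test. Cells of about 3 patients (2/3: 9% to 99%) cannot verify the dose-response assumption.

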7.4.2.3 Hematologic Toxicity

Typically, there is no dosages adjustment related to hematological toxicity with the R-ICE regimen as described in this study. C-R-ICE will be planned to be given on a q 21 - 28 day cycle. C-R-ICE will be postponed until neutrophil counts reach $\geq 1 \times 10^9/L$ and platelet counts $\geq 50 \times 10^9/L$.

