10.2 Imaging, Laboratory and Pathological Studies

Imaging, laboratory and pathological studies will be conducted for staging and response evaluation at baseline, between Cycle 2 Day 15 and Cycle 2 Day 28, and at the end of study evaluation following Cycle 3. Response to treatment will be evaluated according to the International Working Group Response criteria as reported by the revised Cheson criteria (Section 10.3).

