13 STATISTICAL METHODOLOGY

This is single-center, open-label, prospective Phase I/Ib clinical trial evaluating the safety, efficacy, and pharmacokinetics/pharmacodynamics of carfilzomib and standard R-ICE combination therapy in adult patients with relapsed/refractory diffuse large B-cell lymphoma. The statistical design is based on a dose-finding algorithm to determine the maximal tolerated dose (MTD) of the study regimen and an assessment of the efficacy of the treatment for patients as compared to an external standard, i.e., R-ICE historical control. All enrolled patients will receive the study drug and initiation of the treatment should take place as soon as possible following study enrollment. A maximum total of up to 21 evaluable patients will be enrolled in the Phase I of this study, and a total of 9 evaluable patients will be enrolled in the Phase Ib portion of the study. An evaluable subject is defined as a subject who meets eligibility requirements and who does not discontinue prior to end of Cycle 1 for reasons other than DLTs for Phase I or who completes at least 1 cycle of planned therapy for Phase Ib. If a subject signs

an Informed Consent and does not receive treatment, the subject will not be classified as evaluable and will be replaced. Unevaluable patients will be replaced. Analyses will be performed with a focus on estimation of specific clinically important parameters for use in the planning of larger subsequent comparative trials designed to fully assess efficacy and safety.

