13.2 Missing Data

The amount and nature of missing data will be characterized and no method of imputation will be used for missing data. A summary of missing data will be provided according to the number of subjects, the time points where the data are missing, and clinical center. For each clinical center, the number and percent of subjects with no missing data will be presented in tabular form.

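### The response-rate denominator is defined inconsistently, and Section 13.5.2 as written drops and replaces treated patients who fail in Cycle 1

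*Combined protocol and SAP*

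**What the plan says.** Five places in the protocol bear on who is counted in the efficacy analysis.

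- **Section 13.5.2** gives the formal rule for the pooled Phase I and Ib patients: "The evaluable population is defined as patients who meet eligibility requirements and complete at least 1 cycle of therapy. Unevaluable patients will be replaced". The response proportion under test is defined on that population, and for treatment at the maximum tolerated dose (MTD).
- **Section 13** gives a two-part rule. A Phase I patient is evaluable if eligible and if he or she "does not discontinue prior to end of Cycle 1 for reasons other than DLTs for Phase I", so a Cycle 1 DLT discontinuation stays in. A Phase Ib patient must complete a cycle. The replacement rule in Section 7.4.1.3 likewise covers only patients without a DLT.
- **Section 13.1.2**: "The efficacy analysis will include evaluable patients in the Phase I and Phase Ib portions combined".
- **Section 13.5**: "The efficacy analysis will include patients treated in the Phase I and Phase Ib part of the study".
- **The synopsis (Statistical Analysis)** also refers to treated Phase I patients, plus 9 enrolled in the expansion cohort.

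On missing outcomes, Section 13.2 says "no method of imputation will be used for missing data". Section 10.2 schedules imaging "for staging and response evaluation at baseline, between Cycle 2 Day 15 and Cycle 2 Day 28", and again at the end-of-study evaluation after Cycle 3. Section 8.5 requires the end-of-study evaluations whenever treatment is discontinued.

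**The concern.** A Phase I patient who stops in Cycle 1 because of a DLT is evaluable under Section 13 and not under Section 13.5.2. A patient of either phase who progresses, dies or withdraws in Cycle 1 leaves the denominator and is replaced under Section 13.5.2, but is counted if the wording of Section 13.5 is followed. Two analysts could therefore report different denominators for the same primary result.

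The patients removed are likely to include early treatment failures. Dropping them makes the response rate describe those who got through Cycle 1 rather than those who were treated. Section 13 says the estimates are meant for planning larger comparative trials, so bias in the estimate matters even when the test result is clear. The choice is also not blind to data: Sections 13.1.2 and 13.5 say that the efficacy analysis was redesigned after responses in the first 15 patients were seen, with a reported Phase I response rate of 90%.

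**Working it through.** **1. The passages side by side.**

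| Treated, eligible patient | Section 13.5.2 | Section 13 | Section 13.5, synopsis |
|---|---|---|---|
| Phase I, stops in Cycle 1 for a DLT | out, replaced | in | in |
| Phase Ib, stops in Cycle 1 for toxicity | out, replaced | out, replaced | in |
| Either phase, progresses, dies or withdraws in Cycle 1 | out, replaced | out, replaced | in |
| Completes Cycle 1, fails later | in | in | in |

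The conflict needs no arithmetic. The firmest contradiction is the first row, Section 13 against Section 13.5.2. The last row shows that later failures are not lost.

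Section 13.5.2 does not say whether completing a cycle means receiving its doses or reaching the end of the interval. Section 7.4.2.3 says "C-R-ICE will be planned to be given on a q 21 - 28 day cycle". If receiving the doses is enough, the excluded group is smaller.

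**2. The plan's own figures.** Section 13.5.2 states 4.8% type I error and 80.1% power for 50% against 70% with up to 30 patients. The exact one-stage binomial does not give that pair at n = 30:

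- at least 20 responses: 4.94% and 73.0%
- at least 21 responses: 2.14% and 58.9%

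That is a separate problem, and nothing below depends on how it is resolved.

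**3. Effect on the estimate.** Let T be the response rate among all treated patients, f the share excluded and q the response rate of those excluded. The rate among evaluable patients is then

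p = (T − f·q) / (1 − f).

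Assumed, not in the documents: T = 60%; f = 2%, 5% and 10%; q = 0 or 25%.

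| f | q = 0 | q = 25% |
|---|---|---|
| 2% | 0.60/0.98 = 61.2% | 0.595/0.98 = 60.7% |
| 5% | 0.60/0.95 = 63.2% | 0.5875/0.95 = 61.8% |
| 10% | 0.60/0.90 = 66.7% | 0.575/0.90 = 63.9% |

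If q = T, then p = T and there is no bias. With 30 evaluable patients, f = 10% means 30/0.90 ≈ 33 treated, so about three replaced.

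**4. Effect on the conclusion.** The cutoff of 21/30 is used only for illustration, as the smallest that keeps the exact error within 4.8%. With T = 50% and all excluded patients failing, the chance of a positive result is 2.1%, 2.8%, 4.1% and 7.8% at f = 0, 2%, 5% and 10%. It passes 4.8% only above f of about 6.2%, or about 11.7% if excluded patients respond at 25%.

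Adding replaced early failures back as non-responders gives these exact one-sided p-values against 50%:

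- 21/30: 0.021; 21/31: 0.035; 21/32: 0.055
- 22/30: 0.008; 22/33: 0.040
- 24/30: 0.0007; 24/33: 0.007

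Judged against 4.8%, 21/30 survives one restored failure but not two. The results of 22/30 and 24/30 survive three.

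**The case against.** The strongest reply is that an evaluable population is a legitimate choice, stated openly. Section 13.5.2 defines both the population and the parameter, and Section 13.1.2 also says evaluable. The sentence in Section 13.5 is mainly about pooling the phases, so its reference to treated patients may be loose wording. This has force, but the synopsis uses the same word, and it leaves the contradiction with Section 13 untouched.

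That contradiction may affect few patients. Section 7.4.1 lets patients with a DLT continue at the investigator's discretion, and the hematologic DLT in Section 7.4.1.2 is a delay of the next dose, by when Cycle 1 dosing has normally been given. This limits the size but does not reconcile the text.

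A reader might infer that early dropouts cannot be assessed for response, because the first scheduled on-treatment scan falls in Cycle 2. The documents do not support that: Sections 8.5 and 10.2 together should give most living dropouts an end-of-study assessment. A documented progression is data and needs no imputation. The gap is that no rule says how such a patient counts.

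A reader might also infer that the 4.8% error rate is breached. That does not follow. The test keeps its level for the parameter that Section 13.5.2 defines. For treated patients the answer depends on an exclusion rate that the documents do not give. It depends too on whether the 50% control rate in Section 13.5.1 was counted on treated or evaluable patients, which is not stated. If it was counted on a similar evaluable basis, the bias relative to control shrinks or cancels.

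**Conclusion.** The inconsistency stands on the text alone: Section 13 and Section 13.5.2 classify the same Phase I patient differently, and the remaining passages alternate between evaluable and treated. Followed literally, Section 13.5.2 removes Cycle 1 failures from the denominator, and no other passage counts them as non-responders.

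The consequence is moderate. The treated-patient response rate is overstated by about 1 to 7 percentage points in the illustration, assuming a true rate of 60%, 2% to 10% excluded and excluded patients responding at 0 to 25%. A reversal of the conclusion needs a result near the cutoff. Given the 90% reported for Phase I, whose denominator is not stated, such a result may not arise. The point should be corrected for the sake of the estimate and to close an open choice of denominator after responses are known. It does not show that the trial's conclusion would be wrong.

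**What to change.** In Section 13.5.2:

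- Define one primary efficacy population: all eligible patients who receive any carfilzomib in the phases pooled.
- Count every such patient without a documented complete or partial response as a non-responder, including those who progress, die or withdraw in Cycle 1. State that this is part of the endpoint definition and not imputation under Section 13.2.
- Keep replacement for DLT evaluability only, with replaced treated patients retained in the efficacy denominator.
- Report the completed-Cycle-1 set as a sensitivity analysis, and define what completing a cycle means.
- Reconcile the pooled population, which includes Phase I patients from the dose escalation, with the clause that ties the response proportion to the MTD.

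Align the synopsis and Sections 13, 13.1.2 and 13.5 with this text, and record that the definition was set after Phase I responses were known. No cutoff is proposed here. The decision rule and power should be recomputed for the attained number of patients when the separate problem with 4.8% and 80.1% is resolved.

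The cost is protocol and SAP text plus that recalculation. No visits are added, because Section 8.5 already requires evaluations at discontinuation. The response rate may come out slightly lower, because patients who stop early for reasons unrelated to lymphoma also count as non-responders.

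### Section 13.5.2 keeps a two-stage stopping rule with no stage sizes or boundaries and states no success threshold, and its 4.8% / 80.1% cannot be obtained with the 30 patients of the re-design

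*Combined protocol and SAP*

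**What the plan says.** Section 13.5.2 tests a response rate of at most 50% against a rate above 50%, with 70% regarded as promising. On size it says: "A total of up to 30 evaluable patients will be accrued in the Phase I and Phase Ib portions of the study". On error rates it says: "With this re-design, the probability is 4.8% of falsely concluding that the proportion of those who experience an overall response exceeds 50" per cent, and "80.1% is the probability of correctly concluding efficacy when the overall response rate is 70" per cent. It gives no number of responders that would count as success.

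The closing paragraph of the same section then turns to stages. It opens "In the event that the actual first stage sample size is not as planned, the adjustment of the first-stage stopping rule" and refers to the approximate minimax rule of Green and Dahlberg. That rule takes the planned final sample size and the planned final boundary as given. The paragraph ends: "If the planned second stage sample size is not attained, the bound will be adjusted so to preserve Type I error".

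Section 13.1.2 repeats the power claim ("This design requires a total of up to 30 patients in order to achieve approximately 80.1% power to detect differences of 20 percentage points"), as does the Statistical Analysis entry of the synopsis. Section 13.1.2 also records that the Phase Ib sample was reduced to 9 additional patients, and it gives a second total: "The efficacy analysis will include evaluable patients in the Phase I and Phase Ib portions combined (sample size up to 45". Section 13.5 says that pooling was decided after the response rate in the first 15 patients had been seen.

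**The concern.** The re-design is described as one pooled sample and one hypothesis, yet the decision rule is written for two stages. Adjusting a first-stage cut-off needs four planned quantities: first-stage size, first-stage stopping number, total size and final boundary. Only a total is given, and it is given as both 30 and 45.

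Two things are at stake. First, the plan implies an interim futility stop that nobody could carry out. Second, the primary efficacy test has no pre-specified threshold. That matters more than usual here, because the decision to pool was taken with response data in hand. An unstated threshold leaves the conclusion open to a choice made after the results are known.

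**Working it through.** **Inputs.** Null rate 50%, alternative 70%, type I error 4.8% and power 80.1% (section 13.5.2); total 30 (sections 13.1.2 and 13.5.2), with 45 as the competing total (section 13.1.2). The hypotheses are one-sided.

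**Step 1: try to reproduce the stated pair with 30 patients, one stage.** For success at c or more responders, type I error = P(Bin(30, 0.5) ≥ c) and power = P(Bin(30, 0.7) ≥ c).

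| Rule | Type I error | Power at 70% |
|---|---|---|
| ≥ 20 of 30 | 0.0494 | 0.7304 |
| ≥ 19 of 30 | 0.1002 | 0.8407 |

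Neither row is 4.8% / 80.1%. Normal and arcsine approximations at 30 patients give power of 0.72 to 0.77 at one-sided 0.05, and 0.60 to 0.67 at two-sided 0.05.

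**Step 2: try 30 patients, two stages.** Stop if X₁ ≤ r₁ among the first n₁ patients; otherwise continue to n and succeed if total responders exceed r. At response rate p,

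P(success) = Σ over x from r₁+1 to n₁ of P(Bin(n₁, p) = x) × P(Bin(n − n₁, p) > r − x).

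Over all n₁, r₁ and r with n = 30 and type I error at most 0.05, the largest power is 0.7304. A futility stop can only remove successes, so it cannot beat the single-stage rule. To reach power 0.801 with 30 patients, type I error must be at least 0.085. Reading Phase I (n₁ = 21) as the first stage does not help: with success at ≥ 20 of 30, power is again at most 0.7304.

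**Step 3: find where the pair does come from.** The same formula, searched over totals of 25 to 45 (and on to 50), gives two designs that round to 4.8% / 80.1%, both with 37 patients:

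| First stage: stop if | Final: success if | Type I error | Power at 70% |
|---|---|---|---|
| ≤ 12 of 23 | ≥ 24 of 37 | 0.0482 | 0.8011 |
| ≤ 18 of 31 | ≥ 24 of 37 | 0.0479 | 0.8008 |

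The first has the form of a minimax two-stage design, which fits the minimax wording in section 13.5.2. A single-stage exact test also needs at least 37 patients for type I error at most 5% and power at least 80% (≥ 24 of 37: 0.0494 / 0.8071).

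**Step 4: try 45.** The exact single-stage bound is ≥ 29 of 45, with type I error 0.0362 and power 0.8358. That is not the stated pair either.

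**Step 5: exact bounds near the planned size** (smallest c with one-sided type I error at most 5%).

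| Attained n | Success if | Type I error |
|---|---|---|
| 28 | ≥ 19 | 4.36% |
| 29 | ≥ 20 | 3.07% |
| 30 | ≥ 20 | 4.94% |
| 31 | ≥ 21 | 3.54% |
| 33 | ≥ 22 | 4.01% |

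**The case against.** The best defence is that the closing sentence of section 13.5.2 already protects the trial. If the planned second-stage size is missed, the bound is to be adjusted to preserve type I error. Applied to 30 patients, that leads a careful analyst to ≥ 20 of 30 and an error of 4.94%. This stands as far as it goes. It does not supply the missing first-stage rule, and it gives 73.0% power rather than 80.1%.

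For the same reason, a reader might infer that an analyst would carry the 24-responder boundary over to 30 patients, which would give type I error 0.07% and power 16%. The documents do not support that. Neither 24 nor 37 is printed anywhere. The planned final boundary enters only as an assumption for calculating the first-stage cut-off, alongside the assumption that the planned final size is reached.

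A reader might also infer that a 66% chance of stopping early under a true rate of 50% has been lost. That figure belongs to the 12-of-23 first stage. The 18-of-31 design fits equally well and stops with probability 86%, and the documents print neither. The practical loss may also be small. Section 13.1.2 reports a 90% response rate in Phase I. If that refers to the first 15 patients (the denominator is not given), 0.9 × 15 = 13.5, so 13 or 14 responders had been seen, already above the 12 at which the first of these designs would stop.

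Finally, no section says outright that the re-design is single-stage, so supplying a complete two-stage design would be an equally valid repair.

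**Conclusion.** The point holds as a defect in the decision rule. Section 13.5.2 relies on stage sizes and boundaries that are defined nowhere, so its futility rule cannot be run, and no success threshold is stated for the primary efficacy test. The stated error rates do not belong to the 30-patient sample: with type I error held at 5%, power at a true rate of 70% is at most 73.0%, about 7 percentage points below the 80.1% claimed.

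That the paragraph and figures survive from an earlier two-stage design is an inference. It rests on the section's own reference to a re-design, the reduced Phase Ib sample, and the match to 37 patients.

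The calculations assume a fixed sample size, one common response rate across pooled patients, and a one-sided exact binomial test. They make no allowance for the decision to pool having followed a look at the first 15 patients.

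**What to change.** 1. In section 13.5.2, delete the paragraph on first and second stages and state that the re-design is single-stage, with no interim efficacy or futility stop. If two stages are intended, print the first-stage size and stopping number, the total size and the final boundary, with their exact error rates.
2. State the success criterion as the exact one-sided binomial bound for the attained number of evaluable patients: ≥ 19/28, ≥ 20/29, ≥ 20/30, ≥ 21/31, ≥ 22/33.
3. Replace 4.8% / 80.1% in section 13.5.2, and the 80.1% in section 13.1.2 and the synopsis, with the true values. For ≥ 20 of 30 these are type I error 4.9% and power 73.0% at 70%. Deleting the paragraph alone would leave an unsupported power claim.
4. Reconcile 45 with 30 in section 13.1.2, since the bound depends on it (29 of 45 against 20 of 30).

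This changes wording and stated figures only; no patients or procedures are added. The price is that the plan must admit power of about 73% and, if single-stage, the absence of an interim futility stop.
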